## Week 2 Check In

# Week 1 Check In

Week 1 Check In

Time for the 1-minute Blueprint weekly mini-survey!

1. Please select the response that describes how you felt in the past week.

(This is an information screen that requires no response)

Click Next to continue

2. I feel tense or wound up

Response is \*\*one\*\* of:

- Not at all
- Time to time, occasionally
- A lot of the time
- Most of the time

3. I still enjoy the things I used to enjoy

Response is \*\*one\*\* of:

- Definitely as much
- Not quite so much
- Only a little
- Hardly at all

4. I get a frightened feeling like something awful is about to happen

Response is \*\*one\*\* of:

- Not at all
- A little, but it doesn't worry me
- Yes, but not too badly
- Very definitely and quite badly

5. I can laugh and see the funny side of things

Response is \*\*one\*\* of:

- As much as I always could
- Not quite so much now
- Definitely not so much now
- Not at all

6. Worrying thoughts go through my mind

Response is \*\*one\*\* of:

- Only occasionally
- From time to time but not too often
- A lot of the time
- A great deal of the time

7. I feel cheerful

Response is \*\*one\*\* of:

- Most of the time
- Sometimes
- Not often
- Not at all

8. I can sit at ease and feel relaxed

Response is \*\*one\*\* of:

- Definitely
- Usually

- Not often
- Not at all

9. I feel as if I am slowed down

Response is **\*\*one\*\*** of:

- Not at all
- Sometimes
- Very often
- Nearly all of the time

10. I get a sort of frightened feeling like butterflies in the stomach

Response is **\*\*one\*\*** of:

- Not at all
- Occasionally
- Quite often
- Very often

11. I have lost interest in my appearance

Response is **\*\*one\*\*** of:

- I take just as much care as ever
- I may not take quite as much care
- I don't take as much care as I should
- Definitely

12. I feel restless as if I have to be on the move

Response is **\*\*one\*\*** of:

- Not at all
- Not very much
- Quite a lot
- Very much indeed

13. I look forward with enjoyment to things

Response is **\*\*one\*\*** of:

- As much as I ever did
- A bit less than I used to
- Definitely less than I used to
- Hardly at all

14. I get sudden feelings of panic

Response is \*\*one\*\* of:

- Not at all
- Not very often
- Quite often
- Very often indeed

15. I can enjoy a good book or radio or TV program

Response is \*\*one\*\* of:

- Often
- Sometimes
- Not often
- Very seldom

16. How confident do you feel using progressive muscle relaxation?

This question includes an image.

Response is \*\*one position\*\* in this scale:

- 0 (Not at all confident)
- 10
- 20
- 30
- 40
- 50
- 60
- 70
- 80
- 90
- 100 (Extremely confident)

17. That's okay. It is normal to feel a little unsure at first with progressive muscle relaxation. Most people find that their confidence improves with practice. You can do it!

(This is an information screen that requires no response)

18. You are off to a great start. It is normal to feel this way about progressive muscle relaxation at this point. Remember to practice daily. Great work!

(This is an information screen that requires no response)

19. Wow, you really have the hang of progressive muscle relaxation. Remember to keep practicing. Great work!

(This is an information screen that requires no response)

20. How helpful is using progressive muscle relaxation

This question includes an image.

Response is \*\*one position\*\* in this scale:

- 0 (Not at all helpful)
- 10
- 20
- 30
- 40
- 50
- 60
- 70
- 80
- 90
- 100 (Extremely helpful)

21. That's OK. It often takes time to get comfortable with a new skill and see its benefits. Most people find that the more they practice progressive muscle relaxation, the more helpful they find it. Give it a try for awhile longer and see what you think.

(This is an information screen that requires no response)

22. That's great. It sounds like progressive muscle relaxation might be a useful tool for you. Keep practicing—the more you use it, the more helpful it is likely to be.

(This is an information screen that requires no response)

23. Great! It sounds like progressive muscle relaxation is a really useful tool for you. Keep practicing - the more you use it, the more helpful it is likely to be.

(This is an information screen that requires no response)

24. How confident do you feel using pleasant imagery?

This question includes an image.

Response is \*\*one position\*\* in this scale:

- 0 (Not at all confident)
- 10
- 20
- 30
- 40
- 50
- 60
- 70
- 80
- 90
- 100 (Extremely confident)

25. That's okay. It is normal to feel a little unsure at first with pleasant imagery. Most people find that their confidence improves with practice. You can do it.

(This is an information screen that requires no response)

26. You are off to a great start. It is normal to feel this way about pleasant imagery at this point. Remember to practice daily. Great work!

(This is an information screen that requires no response)

27. Wow, you really have the hang of pleasant imagery. Remember to keep practicing. Great work!

(This is an information screen that requires no response)

28. How helpful is using pleasant imagery?

This question includes an image.

Response is \*\*one position\*\* in this scale:

- 0 (Not at all helpful)
- 10
- 20
- 30
- 40
- 50
- 60
- 70
- 80
- 90
- 100 (Extremely helpful)

29. That's OK. It often takes time to get comfortable with a new skill and see its benefits. Most people find that the more they practice pleasant imagery, the more helpful they find it. Give it a try for awhile longer and see what you think.

(This is an information screen that requires no response)

30. That's great. It sounds like pleasant imagery might be a useful tool for you. Keep practicing—the more you use it, the more helpful it is likely to be.

(This is an information screen that requires no response)

31. Great! It sounds like pleasant imagery is a really useful tool for you. Keep practicing - the more you use it, the more helpful it is likely to be.

(This is an information screen that requires no response)

32. Thank you!

(This is a score screen that requires no response)

You have completed the assessment. Click Next to submit your responses.

## Week 2 Check In

Time for the 1-minute Blueprint weekly mini-survey!

1. Please select the response that describes how you felt in the past week .

(This is an information screen that requires no response)

Click Next to continue

2. I feel tense or wound up

Response is \*\*one\*\* of:

- Not at all
- Time to time, occasionally
- A lot of the time
- Most of the time

3. I still enjoy the things I used to enjoy

Response is \*\*one\*\* of:

- Definitely as much
- Not quite so much
- Only a little
- Hardly at all

4. I get a frightened feeling like something awful is about to happen

Response is \*\*one\*\* of:

- Not at all
- A little, but it doesn't worry me
- Yes, but not too badly
- Very definitely and quite badly

5. I can laugh and see the funny side of things

Response is \*\*one\*\* of:

- As much as I always could
- Not quite so much now
- Definitely not so much now

- Not at all

6. Worrying thoughts go through my mind

Response is \*\*one\*\* of:

- Only occasionally
- From time to time but not too often
- A lot of the time
- A great deal of the time

7. I feel cheerful

Response is \*\*one\*\* of:

- Most of the time
- Sometimes
- Not often
- Not at all

8. I can sit at ease and feel relaxed

Response is \*\*one\*\* of:

- Definitely
- Usually
- Not often
- Not at all

9. I feel as if I am slowed down

Response is \*\*one\*\* of:

- Not at all
- Sometimes
- Very often
- Nearly all of the time

10. I get a sort of frightened feeling like butterflies in the stomach

Response is \*\*one\*\* of:

- Not at all
- Occasionally
- Quite often
- Very often

11. I have lost interest in my appearance

Response is \*\*one\*\* of:

- I take just as much care as ever
- I may not take quite as much care
- I don't take as much care as I should
- Definitely

12. I feel restless as if I have to be on the move

Response is \*\*one\*\* of:

- Not at all
- Not very much
- Quite a lot
- Very much indeed

13. I look forward with enjoyment to things

Response is \*\*one\*\* of:

- As much as I ever did
- A bit less than I used to
- Definitely less than I used to
- Hardly at all

14. I get sudden feelings of panic

Response is \*\*one\*\* of:

- Not at all
- Not very often
- Quite often
- Very often indeed

15. I can enjoy a good book or radio or TV program

Response is \*\*one\*\* of:

- Often
- Sometimes
- Not often
- Very seldom

16. Thank you!

(This is a score screen that requires no response)

You have completed the assessment. Click Next to submit your responses.

17. How confident do you feel using pleasant activities ?

This question includes an image.

Response is \*\*one position\*\* in this scale:

- 0 (Not at all confident)
- 10
- 20
- 30
- 40
- 50
- 60
- 70
- 80
- 90
- 100 (Extremely confident)

18. This feeling is pretty normal at first with pleasant activities . You just have to make a plan--and stick with it! You can do it...

(This is an information screen that requires no response)

19. This is a good start. Remember, it can be tough to find the time for pleasant activities . But you deserve it--and it can help. Hang in there...

(This is an information screen that requires no response)

20. Excellent! You are a pleasant activities expert. Keep it going...great work!

(This is an information screen that requires no response)

21. How helpful is using pleasant activities ?

This question includes an image.

Response is \*\*one position\*\* in this scale:

- 0 (Not at all helpful)
- 10
- 20
- 30
- 40
- 50
- 60
- 70
- 80
- 90
- 100 (Extremely helpful)

22. That's OK. Try to keep giving this skill a chance, because the more you take time for pleasant activities , the more you get 'you' time. Give it a try for awhile longer and see what you think.

(This is an information screen that requires no response)

23. Great!. It sounds like pleasant activities are working for you. Keep making the time for these activities, because the more you do the better you could feel.

(This is an information screen that requires no response)

24. Wow! It seems like pleasant activities is a really useful tool for you. Keep taking the time to do these - the more you use it, the more helpful it is likely to be.

(This is an information screen that requires no response)

25. How confident do you feel using activity rest cycle ?

This question includes an image.

Response is \*\*one position\*\* in this scale:

- 0 (Not at all confident)
- 10
- 20
- 30
- 40
- 50
- 60
- 70
- 80
- 90
- 100 (Extremely confident)

26. That's okay because the activity rest cycle can be tough to use at first. Try to focus on one activity at the beginning. This will help your confidence. You can do it!

(This is an information screen that requires no response)

27. You are off to a great start. It is normal not to feel like an activity rest cycle expert at this point. Remember to practice daily. Great work!

(This is an information screen that requires no response)

28. Boom! You really have the hang of the activity rest cycle. Remember to keep practicing. Excellent!

(This is an information screen that requires no response)

29. How helpful is using activity rest cycle ?

This question includes an image.

Response is \*\*one position\*\* in this scale:

- 0 (Not at all helpful)
- 10
- 20
- 30
- 40
- 50
- 60
- 70
- 80
- 90
- 100 (Extremely helpful)

30. It can take a little time to work through a new skill and figure out how it might work best. Most people find that the more they practice activity rest cycle , the more helpful they find it. Give it a try for awhile longer and see what you think.

(This is an information screen that requires no response)

31. Really good! It sounds like activity rest cycle is a good addition to the toolbox. Keep practicing—the more you use it, the more helpful it is likely to be.

(This is an information screen that requires no response)

32. Wonderful! It sounds like activity rest cycle is a keeper for you. Keep practicing - the more you use it, the more helpful it is likely to be.

(This is an information screen that requires no response)

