## Appendix 1: Schedule of Events

	Day 0 (In-Hospital, Baseline)	Day 1 , T1 (Discharge) (+30 days)	Week 1	Week 2	Week 3	Week 4 Day 30, T2 (+60 days)	Day 90 (+30 days), T3
Screening*	X						
Consent (a)*	X						
App Registration*	X						
Baseline Survey (b)*	X						
Usability Survey*							
T1 Survey (c)		X					
T2 Survey (c)						X	
T3 Survey (c)							X
Weekly Check-In (d)			X	X	X		
Progressive Muscle Relaxation and Pleasant Imagery (mCST)			X				
Pleasant Activities and Activity Rest Cycling				X			
Fast Relax and Managing Negative Thoughts						X	
Problem Solving and Maintenance							X
Data Entry (e)	X	X				X	X
AE/SAE assessment (f)	X	X				X	X
Survival Status (f)		X				X	X
End of Study (g)							X

- a) Patients may be approached and consented during their admission, if well enough; their hospitalization (e.g., while in step-down), or within 1-3 days of returning to their home for participation in the study
- b) Completion of the baseline survey includes the patient providing self-reported information such as social and demographic information and general health status.
- c) Surveys 1, 2 and 3 will be completed via the app by all study participants, regardless of arm assignments. Patients who are assigned to the control arm will be alerted when it is time to complete their T2 and T3 via app notification.
- d) For those participants assigned to Arm 1 or 2, they will complete a weekly check-in to ascertain overall safety of the patient and usefulness of coping skills practice.
- e) AE/SAE assessment and survival status will be completed via EMR review and/or telephone interview.
- f) Study completion for patients enrolled in the study is considered to occur at the completion of T3. However, participants may undergo EOS if they are withdrawn from the study by the PI or opt to withdraw from the study voluntarily at any time. Should withdraw of a patient occur, the reason for withdraw and date of withdraw will be documented. AE/SAEs and survival status will be noted, as applicable.

\*For aim 1 only.

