You have completed the assessment. Click Next to submit your responses.

17. How confident do you feel recognizing unhelpful thoughts ?

This question includes an image.

Response is \*\*one position\*\* in this scale:

- 0 (Not at all confident)
- 10
- 20
- 30
- 40
- 50
- 60
- 70
- 80
- 90
- 100 (Extremely confident)

18. This is totally normal. Try to work on recognizing unhelpful thoughts when you are in certain situations or places. Your confidence will improve as you practice. You can do it!

(This is an information screen that requires no response)

19. OK, really good start! Everybody struggles a bit with recognizing unhelpful thoughts at this point. Remember to practice using positive coping thoughts . Great work!

(This is an information screen that requires no response)

20. Wow, you really have the hang of using coping thoughts to replace negative thoughts. Remember to keep practicing. Great work!

(This is an information screen that requires no response)

21. How helpful is recognizing unhelpful thoughts ?

This question includes an image.

Response is \*\*one position\*\* in this scale:

- 0 (Not at all helpful)
- 10
- 20
- 30
- 40
- 50
- 60
- 70
- 80
- 90
- 100 (Extremely helpful)

22. That's OK. But before you give up on using positive coping thoughts , remember that many people start to see the benefits after a couple of weeks or more. Give it a try for awhile longer and see what you think.

(This is an information screen that requires no response)

23. That's great. It seems like you are having success with recognizing unhelpful thoughts . Keep practicing the positive coping thoughts —the more you use them, the more helpful they will be in tough situations.

(This is an information screen that requires no response)

24. Fantastic! It seems like recognizing unhelpful thoughts and replacing them with positive coping thoughts is another keeper for you. Keep practicing - the more you do, the more confident you'll be-- and the more helpful it is likely to be.

(This is an information screen that requires no response)

25. How confident do you feel using fast relax ?

This question includes an image.

Response is \*\*one position\*\* in this scale:

- 0 (Not at all confident)
- 10

- 20
- 30
- 40
- 50
- 60
- 70
- 80
- 90
- 100 (Extremely confident)

26. This is OK. Fast relax is a brief skill, but can take some practice. Try using cues during the day (phone rings, you sit down, etc) to remind yourself to use it. You can do it!

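### The Week 2 and Week 3 check-in forms print the completion screen before the skill ratings, so a patient who stops there leaves four skills unrated that week, two of them for good

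*Protocol*

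**What the plan says.** Protocol Appendix 3, part J prints the weekly check-ins item by item. In the Week 2 form, items 2 to 15 are the HADS and item 16 is a score screen reading "You have completed the assessment. Click Next to submit your responses". The next item is "17. How confident do you feel using pleasant activities". The form then continues to item 32 with the helpfulness of pleasant activities, "How confident do you feel using activity rest cycle", the helpfulness of activity rest cycle, and feedback screens. The Week 3 form has the same structure: the same screen at item 16, followed by "17. How confident do you feel recognizing unhelpful thoughts" and then the ratings of fast relax. Neither form has a closing screen after item 32.

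The Week 1 form has the opposite order: ratings and feedback are items 16 to 31, and the completion screen is item 32.

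The first form under the Week 2 heading is titled "Week 1 Check In" and repeats the Week 1 HADS and Week 1 skill ratings. The form for the week 2 skills follows it.

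On purpose, Protocol Appendix 1, note d says of patients in Arms 1 and 2 that "they will complete a weekly check-in to ascertain overall safety of the patient and usefulness of coping skills practice". Protocol section 9 plans exploratory models that include self-efficacy as a mechanistic element.

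**The concern.** A patient is told the check-in is finished while half of it is still to come. The survey is introduced as taking one minute, so stopping at that message would be a natural response. Those who carry on are probably more engaged with the program, so the ratings of the week 2 and week 3 skills could come from a selected group, while week 1 skills are rated by everyone who completes that form.

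At stake is the pilot's information on which skills patients found useful and felt able to use. The confidence ratings are also the closest thing to a self-efficacy measure in the forms printed after T1, since the T2 and T3 surveys do not ask about confidence in the skills.

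**Working it through.** No power or precision figure is involved. The check is a count of items in the printed forms.

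**Skills taught** (Protocol section 3): 2 in week 1, 2 in week 2, 2 in week 3 and 1 in week 4, so 2 + 2 + 2 + 1 = 7.

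**Skill ratings by form** (Protocol Appendix 3, part J, leaving out the repeated Week 1 form):

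| Form | Skills rated | Ratings | Position of completion screen | Ratings after it |
|---|---|---|---|---|
| Week 1 | Progressive muscle relaxation, pleasant imagery | 4 | Item 32, last | 0 |
| Week 2 | Pleasant activities, activity rest cycle | 4 | Item 16 | 4 |
| Week 3 | Unhelpful thoughts, fast relax | 4 | Item 16 | 4 |
| Week 4 | Unhelpful thoughts, fast relax (again) | 4 | None | 0 |
| Total | | 16 | | 8 |

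So 8 of 16 ratings (50%) follow the early screen, and they cover 4 of the 7 skills. No form rates problem solving.

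**Which of the four skills have another rating?** Unhelpful thoughts and fast relax are asked again in Week 4, with no completion screen before them. Pleasant activities and activity rest cycle appear in no other form. Ratings with no second chance are therefore 2 skills × 2 ratings = 4 of 16.

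**How good is the Week 4 repeat?** Its two helpfulness items carry response anchors worded in terms of confidence. For all four skills, the only helpfulness rating with matching anchors is therefore the one after the early screen.

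**Scale across the trial.** The protocol plans 25 + 25 = 50 app patients, which gives 50 × 8 = 400 of 50 × 16 = 800 ratings after the screen. The SAP targets 15 + 15 = 30 app patients, which gives 30 × 8 = 240 of 30 × 16 = 480. These are ratings placed after the screen, not ratings lost.

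**What lies before the screen.** All 14 HADS items (2 to 15) precede item 16 in both forms, so no HADS item is behind it.

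**Is the order deliberate?** In every other form with a score screen, no question follows it: baseline item 34, T1 item 100, T2 item 112, T3 item 102 and Week 1 item 32. Only the Week 2 and Week 3 forms put questions after it, which points to a slip in assembly.

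No loss of precision is calculated, because the documents give neither a standard deviation for the ratings nor a rate of stopping.

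**The case against.** The strongest reply is that the screen tells the patient to click Next, and in this app Next need not end a survey. In the baseline, T1, T2 and T3 surveys the score screen is followed by another screen. By that logic a patient who obeys item 16 arrives at item 17, and data are lost only if the patient closes the form instead. The appendix is also a listing of items, not a map of navigation. It prints alternative feedback screens one after another, puts the T1 not-eligible and enrolled messages side by side, and jumps from item 63 to item 78 in T1. This stands: the printed order cannot prove that ratings are lost. It does not remove the defect, because what follows the score screen in the other surveys is only a closing information screen, never a question.

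A second reply is that no planned result depends on these ratings. The SAP does not list them among its outcomes (section 3.1), its table of other variables (section 3.3) is empty, and its planned tables do not include them. Nothing ties the self-efficacy analysis in Protocol section 9 to these particular items, and choosing between skills is not a stated aim. This also stands and limits the point to a small one.

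A third reply is that Aim 1 usability testing and the prompts for incomplete data would catch the problem. This is weaker. The tasks listed for the Aim 1 visit do not name the weekly check-ins. The incomplete-data prompts are shown to the study team. Forced responses are described for key items such as the primary outcome surveys, and nothing extends them to skill ratings.

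**Conclusion.** The screen order in the Week 2 and Week 3 forms is inconsistent with Week 1 and should be corrected. Half of the skill ratings (8 of 16) follow a message that the check-in is complete. For a patient who stops at it in both weeks, pleasant activities and activity rest cycle go unrated altogether. Unhelpful thoughts and fast relax lose their week 3 rating and keep only the imperfectly anchored Week 4 one, provided the patient completes that form. How many patients would stop is unknown.

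A reader might infer more, and the documents do not support it:

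- **Ratings of four of the seven skills are lost.** Navigation is not shown, and Week 4 asks about two of the four again.
- **Two thirds of the ratings are at risk.** That is 8 of 12 and omits the four ratings in Week 4.
- **Week 2 has two HADS assessments.** Protocol section 3 describes one HADS a week and the schedule shows one check-in per week. The repeated form keeps its Week 1 title and content, so it is probably a paste error.
- **The distress or safety data are damaged.** Every HADS item comes before the screen, and the SAP's model uses T1, T2 and T3 only.

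The effect is confined to the check-in's stated purpose of judging usefulness of skills practice and, if these items are meant to feed it, the exploratory self-efficacy analysis.

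**What to change.** In the Week 2 and Week 3 forms, move the score and submit screen from item 16 to follow the present item 32, as in Week 1. No rating would then follow a completion message (0 of 16 instead of 8 of 16). Remove the repeated Week 1 form under the Week 2 heading, so that week 2 has one form with one HADS and the week 2 skills.

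If the forms have already been used in this order, report the number of patients rating each skill and treat comparisons between week 1 skills and later skills with caution.

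The cost is one screen moved in two app forms and an appendix correction, plus deletion of the duplicate form if it exists in the app. Patients answer nothing extra.
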